7.1.2 ADMINISTRATION AND/OR DOSING

In this study, participants receive access to the intervention on the first day of the study if randomized to the intervention group. Participants will have access to the intervention for the full 56-63 days of the study period. At the conclusion of the study period, both the control and intervention groups will continue to have access to the same version of the Smoke Free app to which they had access during the study.

7.2 FIDELITY

7.2.1 INTERVENTIONIST TRAINING AND TRACKING

N/A

7.3 MEASURES TO MINIMIZE BIAS: RANDOMIZATION AND BLINDING

Participants will be digitally randomized in a 1:1 ratio to a core version of the Smoke Free app plus the game module or to a core version of the Smoke Free app. Allocation, concealed from investigators, will be performed using a random number generator with a random seed in the Smoke Free app platform.

Randomization will be stratified by age (<50 years old and \geq 50 years old) and by smoking intensity (<5 cigarettes per day and \geq 5 cigarettes per day on average), to facilitate assessment of effect modification.

The randomization will occur immediately after participants provide consent to participate in the study. Participants will not be able to navigate past an onboarding screen until they complete the screening questionnaire and are found to be eligible and provide consent to participate. Once they have provided consent, they will be able to advance past the onboarding screen and will automatically be granted access to the app version for their assigned study group.

Assessors of the follow-up cotinine test to assess smoking status will be blinded; others will not be.

7.4 STUDY INTERVENTION/EXPERIMENTAL MANIPULATION ADHERENCE

N/A

7.5 CONCOMITANT THERAPY

During the pilot trial, participants may also use alternative smoking cessation methods, including over-the-counter and prescribed medications. Use of alternative smoking cessation methods will be assessed in the follow-up questionnaire.

7.5.1 RESCUE THERAPY

N/A

8 STUDY INTERVENTION/EXPERIMENTAL MANIPULATION DISCONTINUATION AND PARTICIPANT DISCONTINUATION/WITHDRAWAL

8.1 DISCONTINUATION OF STUDY INTERVENTION/EXPERIMENTAL MANIPULATION

When a subject discontinues using the Smoke Free app, but does not drop out of the study, remaining study procedures will be completed as indicated by the study protocol. The participant is able to stop using the Smoke Free app at any time without taking any further action.

8.2 PARTICIPANT DISCONTINUATION/WITHDRAWAL FROM THE STUDY

Participants are free to withdraw from participation in the study at any time upon request. If a participant chooses to withdraw from the study, the participant can send an email to the study email address ([contact]). Instructions on withdrawal and a link to the study email account will also be provided in the help section of the Smoke Free app. If a participant withdraws, the study team will inform the Smoke Free app to stop collecting user data for study purposes. Smoke Free may continue to collect routine user data. Former participants will then be able to continue using the same version of the Smoke Free app that they received as part of the study.

The investigator will not discontinue a participant from the study for any reason.

The reason for participant discontinuation or withdrawal from the study will be recorded on the Case Report Form (CRF). Subjects who consent to participate in the study and are randomized but do not receive the study intervention may be replaced. This may occur if there is an error in the Qualtrics survey programming, the Qualtrics API, or the Smoke Free software code. Subjects who consent to participate in the study and are randomized and receive the study intervention, and subsequently withdraw, will not be replaced.

8.3 LOST TO FOLLOW-UP

A participant will be considered lost to follow-up if he or she fails to complete the follow-up questionnaire within 7 days or, if invited, the saliva cotinine test after at least 3 attempts of contact via text message.

The following actions must be taken if a participant fails to return to the clinic for a required study visit:

- Before a participant is deemed lost to follow-up, the investigator or designee will make every effort to regain contact with the participant (where possible, 3 text messages to the participant's last known phone number). The e-mails will be sent every other day, and the text message will be sent the day after the third e-mail. These contact attempts will be documented in the participant's study file.
- Should the participant continue to be unreachable, he or she will be considered to have withdrawn from the study with a primary reason of lost to follow-up.

9 STUDY ASSESSMENTS AND PROCEDURES

9.1 ENDPOINT AND OTHER NON-SAFETY ASSESSMENTS

Participants will be randomized in a 1:1 ratio to the core Smoke Free app plus the gamified module or to the core Smoke Free app. Individuals will be invited to participate in the pilot trial in the initial onboarding screens within the Smoke Free smartphone app, with a link to a screening questionnaire and consent form in Qualtrics. The randomization will occur immediately after participants provide consent to participate in the study. Participants will not be able to navigate past an onboarding screen in Smoke Free until they complete the screening questionnaire and are found to be eligible and provide consent to participate. Once they have provided consent, they will be able to advance past the onboarding screen and will automatically be granted access to the app version for their assigned study group.

After consenting, participants will receive an e-mail with a link to the baseline questionnaire in Qualtrics.

Participation will last until 56 days after the person's selected quit day. During this time, participants may use the app as they wish, and the app will passively collect information on app engagement.

At the end of the 56-day period, participants will be asked to complete a follow-up questionnaire in Qualtrics. Those reporting in the follow-up questionnaire having been abstinent for 7 days will be mailed a salivary cotinine test kit to upload photos of the test results that biochemically verify smoking status.

9.2 SAFETY ASSESSMENTS

N/A

9.3 ADVERSE EVENTS AND SERIOUS ADVERSE EVENTS

9.3.1 DEFINITION OF ADVERSE EVENTS

OHRP defines an adverse event (AE) as any untoward or unfavorable medical occurrence in a human subject, including any abnormal sign (for example, abnormal physical exam or laboratory finding), symptom, or disease, temporally associated with the subject's participation in the research, whether or not considered related to the subject's participation in the research (modified from the definition of adverse events in the 1996 International Conference on Harmonization E-6 Guidelines for Good Clinical Practice).

AEs will be recorded in a spreadsheet, and the PI will monitor these events to grade severity, relationship to the study intervention, and to assess whether the nature, severity, frequency is unexpected, and thus warrants reporting as an unanticipated problem.

9.3.2 DEFINITION OF SERIOUS ADVERSE EVENTS

A serious adverse event (SAE) is one that meets one or more of the following criteria:

- Results in death.
- Is life-threatening (places the subject at immediate risk of death from the event as it occurred).
- Results in inpatient hospitalization or prolongation of existing hospitalization.
- Results in a persistent or significant disability or incapacity.
- Results in a congenital anomaly or birth defect.
- An important medical event that does not result in death, be life threatening, or require hospitalization may be considered an SAE when, based upon appropriate medical judgment, the event may jeopardize the subject and may require medical or surgical intervention to prevent one of the outcomes listed in this definition.

9.3.3 CLASSIFICATION OF AN ADVERSE EVENT

9.3.3.1 SEVERITY OF EVENT

All reportable AEs will be assessed by a study PI or co-investigator using the following guidelines to quantify intensity:

1. Mild: events require minimal or no treatment and do not interfere with the participant's daily activities.
2. Moderate: events result in a low level of inconvenience or concern with the therapeutic measures. Moderate events may cause some interference with functioning.
3. Severe: events interrupt a participant's usual daily activity and may require systemic drug therapy or other treatment. Severe events are usually incapacitating

9.3.3.2 RELATIONSHIP TO STUDY INTERVENTION/EXPERIMENTAL MANIPULATION

To assess relationship of an event to study intervention, the following guidelines are used:

1. Related (Possible, Probable, Definite)
 - a. The event is known to occur with the study intervention.
 - b. There is a temporal relationship between the intervention and event onset.
 - c. The event abates when the intervention is discontinued.
 - d. The event reappears upon a re-challenge with the intervention.
2. Not Related (Unlikely, Not Related)
 - a. There is no temporal relationship between the intervention and event onset.
 - b. An alternate etiology has been established.

9.3.3.3 EXPECTEDNESS

The study PI will be responsible for determining whether an AE is expected or unexpected. An AE will be considered unexpected if the nature, severity, or frequency of the event is not consistent with the risk information previously described for the intervention.

9.3.4 TIME PERIOD AND FREQUENCY FOR EVENT ASSESSMENT AND FOLLOW-UP

AEs and SAEs will be recorded in the data collection system throughout the study. Events will be followed for outcome information until resolution or stabilization.

The Study PI will record all reportable events with start dates occurring any time after informed consent is obtained until seven (for non-serious AEs) or 30 days (for SAEs) after the last day of study participation. In the 2-month follow-up questionnaire, participants will be asked to report the occurrence of AE/SAEs since study enrollment in an open-ended format.

9.3.5 ADVERSE EVENT REPORTING

In the unlikely event that an AE or SAE incident occurs during this study, any AE meeting the specified SAE criteria will be submitted within 10 workdays of the PI's awareness in the UCSF electronic IRB system to the UCSF CHR. This process applies to both initial and follow-up SAE reports.

9.3.6 SERIOUS ADVERSE EVENT REPORTING

See Section 8.3.5 above.

9.3.7 REPORTING EVENTS TO PARTICIPANTS

N/A

9.3.8 EVENTS OF SPECIAL INTEREST

N/A

9.3.9 REPORTING OF PREGNANCY

N/A

9.4 UNANTICIPATED PROBLEMS

9.4.1 DEFINITION OF UNANTICIPATED PROBLEMS

This protocol uses the definition of Unanticipated Problems as defined by the Office for Human Research Protections (OHRP). OHRP considers unanticipated problems involving risks to participants or others to include, in general, any incident, experience, or outcome that meets all of the following criteria:

- Unexpected in terms of nature, severity, or frequency given (a) the research procedures that are described in the protocol-related documents, such as the Institutional Review Board (IRB)-approved research protocol and informed consent document; and (b) the characteristics of the participant population being studied;
- Related or possibly related to participation in the research (“possibly related” means there is a reasonable possibility that the incident, experience, or outcome may have been caused by the procedures involved in the research); and
- Suggests that the research places participants or others at a greater risk of harm (including physical, psychological, economic, or social harm) than was previously known or recognized.

9.4.2 UNANTICIPATED PROBLEMS REPORTING

Incidents or events that meet the OHRP criteria for UPs require the creation and completion of a UP report form. OHRP recommends that PIs include the following information when reporting an AE, or any other incident, experience, or outcome as an UP to the IRB:

- Protocol identifying information: protocol title and number, PI’s name, and the IRB project number
- A detailed description of the event, incident, experience, or outcome
- An explanation of the basis for determining that the event, incident, experience, or outcome represents an UP

- A description of any changes to the protocol or other corrective actions that have been taken or are proposed in response to the UP

To satisfy the requirement for prompt reporting, UPs will be reported using the following timeline:

- UPs will be reported to the UCSF IRB and to NIH National Institute on Aging and NIH National Cancer Institute within 10 working days of the PI becoming aware of the event, unless life-threatening or resulting in death in which case they will be reported within 24 hours.
- All UPs should be reported to appropriate institutional officials (as required by UCSF's written reporting procedures), the supporting agency head (or designee), and the OHRP within one month of the IRB's receipt of the report of the problem from the PI.

9.4.3 REPORTING UNANTICIPATED PROBLEMS TO PARTICIPANTS

N/A

10 STATISTICAL CONSIDERATIONS

10.1 STATISTICAL HYPOTHESES

- Primary Endpoint(s):

App opens:

- Our null hypothesis: No difference between intervention and control participants in mean number of app opens through the end of the 56-63 day program.
- Primary alternate hypothesis: Intervention and control participants differ in mean number of app opens through the end of the 56-63 day program.

Minutes per session:

- Our null hypothesis: No difference between intervention and control participants in mean number of minutes per session through the end of the 56-63 day program.
- Primary alternate hypothesis: Intervention and control participants differ in mean number of minutes per session through the end of the 56-63 day program.

- Secondary Endpoint(s):

Secondary hypotheses relate to differences between intervention and control participants in the secondary outcomes. (See Section 3.)

10.2 SAMPLE SIZE DETERMINATION

The pilot trial sample size is powered to detect meaningful differences in our primary outcome of number of times the app is opened.

As this is a pilot study, a main objective will be to provide empirical data for effect size estimation for a future full-scale RCT. Thus, our sample size is based on budget and feasible accrual during the study timeline.

With two parallel groups, the sample size calculation was conducted for one of our primary outcomes, a continuous measure of the number of times the Smoke Free app was opened through Day 56 of the study period.

We anticipate that a sample size of 500, with an assumed 70% retention, toward the high end for app-based smoking cessation trials,^{19, 39} will yield a final sample size of 350 at the final assessment. We further anticipate a mean number of app opens of 30.0 per participant and a standard deviation of 45.0 in the core app, based on recent data from users of Smoke Free. A sample size of 350 participants will allow us to detect a between-group difference in app opens, one of the primary outcomes, of 13.5 at 80% power ($\alpha=0.05$).

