1.2 SCHEMA

1.3 SCHEDULE OF ACTIVITIES

Please see schematic of study design above.

Individuals will complete the screening questionnaire when they first open the Smoke Free app (Day 0). Informed consent occurs at the end of the screening questionnaire. Randomization occurs immediately following the screening questionnaire within the Smoke Free app. A link to the baseline questionnaire will be sent on Day 0. Participants have until Day 7 to complete the baseline questionnaire. The person's quit date will occur on Day 0-7 (within 7 days of enrollment). Objective data will be passively collected in the app from enrollment until 8 weeks after the person's initial quit date (Day 56-63). Eight weeks post-

quit date (in Day 56-63), the person will receive an email link to the follow-up questionnaire. If the person reports having abstained from smoking for 7 or more days, they will be mailed the same or next business day a saliva cotinine test kit sent by 2-day mail (arriving Day 58-68). The participant will complete the saliva test within 7 days. Thus, the 2-month assessment will be completed between Day 58-75.

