4 OBJECTIVES AND ENDPOINTS

OBJECTIVES	ENDPOINTS	JUSTIFICATION FOR ENDPOINTS
Primary	
Primary Endpoints:
 
Engagement:
 
 1. Number of unique app sessions: number of times the app was opened; passively collected by the app and averaged in analysis to calculate mean number of app opens by study group over the study period. A new session is defined as use of the app after at least 30 minutes of inactivity. 2. Minutes of app usage per session: passively collected by the app and averaged in analysis among those with a session to calculate mean number of minutes of usage per session by study group. 	
The game intervention is designed to increase the engagement of users, either in terms of the number of times the user interacts with the app or the time spent with the app each time the person opens the app. These endpoints have been used in prior trials of smartphone-based cessation interventions.³⁶ Increased engagement in the quit attempt, in turn, is expected to be associated with increases in program retention, program adherence, and smoking abstinence.

Secondary	
Secondary Endpoints:
 
 1. Engagement: number of unique days with at least one app session. 2. Early efficacy: 
 a. Self-reported 7-day point-prevalence smoking abstinence at 2 months post-quit date; proportion of participants who report having abstained for the prior 7 days during the 2-month follow-up assessment. Recoded to 0 if the person reported having smoked during the last 7 days during repeated measurement of daily smoking in the app. b. Self-reported 30-day point-prevalence smoking abstinence at 2 months post-quit date [early efficacy]: Proportion of participants who report having abstained for the prior 30 days during the 2-month follow-up assessment. Recoded to 0 if the 	
 • Early efficacy, as measured by short-term smoking abstinence, is assumed to mediate the relationship between user engagement with the app and long-term smoking abstinence. • User satisfaction is a measure of the acceptability of the intervention for users.

OBJECTIVES	ENDPOINTS	JUSTIFICATION FOR ENDPOINTS

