5 STUDY DESIGN

5.1 OVERALL DESIGN

The pilot trial will be a two-arm randomized trial of 500 adult users of the Smoke Free app. We will set a quota to include at least 100 individuals age ≥ 50 years old to explore differential program effects by age. The goal of the pilot trial is to assess whether a video game increased engagement with the app, relative to a version of the app without the game. The primary outcome is the number of app opens per participant.

Our primary hypothesis is that the app with the game will increase a user’s engagement, as objectively measured by number of unique app sessions and average minutes of app usage per session. Our secondary hypotheses are that the app with the game will increase retention, early efficacy, and program adherence (use of core app features).

During the study period, participants will be randomized in a 1:1 ratio to the core version of the Smoke Free app plus the game module or to the same core version of the Smoke Free app without the game module (a two-arm trial). Assessors of the follow-up cotinine test to assess smoking status will be blinded; other research personnel will not be. Individuals will be invited to participate in the pilot trial in the initial onboarding screens within the Smoke Free smartphone app, with a link to a screening questionnaire and consent form in Qualtrics. We will recruit individuals age ≥ 18 years old living in the US who smoke at least 1 cigarette per day and have downloaded the Smoke Free app, plan to quit smoking within 7 days, are able to speak, read, and write in English, and are willing to provide a saliva test sample. Participation will last until 8 weeks (56 days) after the person’s selected quit day.

Participants will be asked to complete a baseline questionnaire in Qualtrics after consenting to participate in the study and a follow-up questionnaire in Qualtrics at the end of the 56-day period. Those reporting being smoke-free in the follow-up questionnaire will be mailed a salivary cotinine test kit to upload photos of the test results that biochemically verify smoking status.

The main engagement analyses will be conducted on an intent-to-treat basis using all randomized participants. Regression models will adjust for a range of potential confounders, including gender, age, race/ethnicity, cigarettes per day at baseline, and years smoked.

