10.3 POPULATIONS FOR ANALYSES

The main analyses (i.e., for primary endpoints), unless otherwise noted, will be performed on an intent-to-treat basis that include all randomized participants.

The main analysis of smoking abstinence will be performed on a complete-case basis, using all available outcome data in the modeling with treatment condition as randomized. Sensitivity analyses will be performed 1) on an intent-to-treat basis imputing missing as smoking and 2) using multiple imputation with chained equations to handle missing data. This analytic strategy is consistent with expert recommendations and statistical practice,⁴⁰ because the assumption of missing = smoking may be biased in favor of the group with lower attrition.⁴¹⁻⁴³

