10.4 STATISTICAL ANALYSES

10.4.1 GENERAL APPROACH

The main analyses will be conducted on an intent-to-treat basis using all randomized participants. Adjusted regression models described below will adjust for a range of potential confounders, including gender, age, race/ethnicity, baseline smoking intensity, and years smoked. Multiple imputation using chained equations (MICE) for arbitrary missingness patterns^{44, 45} will be used for sensitivity analyses. In further analyses, we will estimate adjusted regression models on a per-protocol basis.

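### Section 10.2 computes the detectable difference in app opens on the 350 expected at follow-up, but the planned test uses app logs from all 500 randomised: on the plan's own inputs it is about 11.3 opens, not 13.5.

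*Combined protocol and SAP*

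**What the plan says.** Section 10.2 starts from 500 participants and assumes 70% retention, which "will yield a final sample size of 350 at the final assessment". It then gives its distributional inputs: "We further anticipate a mean number of app opens of 30.0 per participant and a standard deviation of 45.0 in the core app". From these it concludes: "A sample size of 350 participants will allow us to detect a between-group difference in app opens, one of the primary outcomes". The difference it reports is 13.5, for 80% power with alpha 0.05. No other power statement appears in the plan.

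The measurement of app opens is described elsewhere. Section 4 defines the endpoint as "passively collected by the app and averaged in analysis to calculate mean number of app opens by study group over the study period". Section 1.3 gives the window: "Objective data will be passively collected in the app from enrollment until 8 weeks after" the initial quit date. Section 9.1 repeats that collection is passive, and Section 11.1.3 says the app operator gathers usage for the 56-63 day period.

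The analysis set is stated three times:
- Section 5.1: "The main engagement analyses will be conducted on an intent-to-treat basis using all randomized participants".
- Section 10.3: "The main analyses (i.e., for primary endpoints), unless otherwise noted, will be performed on an intent-to-treat basis that include all randomized participants".
- Section 10.4.1: "The main analyses will be conducted on an intent-to-treat basis using all randomized participants".

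Sections 10.3 and 10.4.3 specify complete-case analysis for smoking abstinence, not for app opens.

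**The concern.** The 70% is retention at the final assessment, meaning the follow-up questionnaire and, where applicable, the saliva test. That rate limits abstinence and satisfaction, which need a response. It does not limit a count that the app records without any action by the participant. Section 10.2 therefore gives a detectable difference for a group that is not the plan's primary analysis set.

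The trial is not underpowered as a result. What is at stake is that a reader will take 13.5 as the sensitivity of the primary comparison and will misjudge its precision. This matters because Section 10.2 says the sample is powered on this outcome, and also names effect-size estimation for a later full-scale trial as a main objective.

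**Working it through.** **Inputs**
- SD 45.0 (Section 10.2, given for the core app only; taken here as common to both arms).
- Alpha 0.05 and power 80% (Section 10.2). Two-sided is inferred from the non-directional alternative in Section 10.1.
- Allocation 1:1 (Section 7.3).
- Randomised N 500; retained N 500 × 0.70 = 350 (Section 10.2).

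**Formulas**, with n per arm:
- SE = SD × √(2/n)
- Detectable difference = (1.960 + 0.842) × SE
- Power for 13.5 = Φ(13.5/SE − 1.960)
- 95% CI half-width = 1.960 × SE

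**The plan's figure first (N = 350, n = 175)**
- SE = 45 × √(2/175) = 4.811.
- Detectable difference = 2.802 × 4.811 = 13.48, or 13.51 with the noncentral t.
- In reverse, n = 2 × (2.802 × 45/13.5)² = 174.4, so 175 per arm.

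The 13.5 reproduces, so it rests on 350. A one-sided test would give 11.96, which does not match.

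**The planned analysis set (N = 500, n = 250)**
- SE = 45 × √(2/250) = 4.025.
- Detectable difference = 2.802 × 4.025 = 11.28, or 11.30 with the noncentral t.

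| | N = 350 | N = 500 |
|---|---|---|
| Detectable difference (opens) | 13.48 | 11.28 |
| In SD units | 0.30 | 0.25 |
| Power for 13.5 | 80.1% | 91.8% |
| 95% CI half-width (opens) | 9.43 | 7.89 |

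The ratio 13.48/11.28 equals √(500/350) = 1.195. It is the same for any pair of arm SDs that are held fixed between the two calculations.

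**Would follow-up loss remove app counts?** The documents give no reason to think so:
- Section 8.3 defines loss to follow-up as a missed questionnaire or saliva test. Section 1.3 sends the questionnaire 8 weeks after the quit date, when logging ends.
- Under Section 8.1, someone who stops using the app stays in the study, and so still has a count.
- The only stated event that stops study logging is withdrawal (Section 8.2).

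**Sensitivity to usable N** (assumed values, SD 45)
- N = 450: 2.802 × 45 × √(2/225) = 11.9.
- N = 400: 2.802 × 45 × √(2/200) = 12.6.
- The full 30% loss, N = 350, is needed to return to 13.5.

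**Sensitivity to SD** (assumed values, N = 500)
- SD 40: 10.0. SD 50: 12.5. SD 55: 13.8. SD 60: 15.0.
- The common SD would have to be about 53.9 for 13.5 to be the detectable difference at N = 500.

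**The case against.** The strongest reply has four parts.

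1. **The sentence is conditional and true as written, and deflating for attrition is a familiar cautious choice.** The arithmetic for 350 is right. But Section 10.2 does not present it as deliberate caution. It derives the 350 from retention at an assessment that does not supply the outcome.

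2. **Usable N may be below 500.** The primary test is an adjusted linear model, and multiple imputation is reserved for sensitivity analyses. The age and cigarettes-per-day categories are known at randomisation. The source of gender, race/ethnicity and years smoked is not stated, and if any of them comes from the baseline questionnaire, non-completers could drop out. This stands as a caveat on the 11.3. It does not justify 350: Section 10.2 never cites it, and the documents give no figure for such losses.

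3. **Section 8.3 treats unreachable participants as withdrawn, and Section 8.2 stops data collection on withdrawal.** That status arises only once the logging window has closed. Discarding counts already recorded would contradict the three intent-to-treat statements.

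4. **The game arm may have a larger SD.** Suppose, as an assumption, that it keeps the core app's ratio of SD to mean, 45/30 = 1.5. The detectable difference d then solves d = 2.802 × √[(45² + (1.5 × (30 + d))²)/n]. This gives 14.2 at N = 500, with 77% power for 13.5. The same assumption gives 18.0 at N = 350, so it undermines the plan's figure equally and leaves the N mismatch conservative. What stands is that neither 11.3 nor 13.5 is conservative with respect to the SD.

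**Conclusion.** The concern holds. The plan's only power statement does not describe its primary analysis. With SD 45 in both arms, two-sided alpha 0.05, 1:1 allocation and all 500 contributing, the detectable difference at 80% power is about 11.3 opens, and power for 13.5 is about 92%. The mismatch in N alone overstates the detectable difference by about 20% when SDs are held fixed. The mismatch itself is certain from the text. The replacement value depends on the SD assumption and on how many participants have usable data; covariate adjustment is ignored, as it is in Section 10.2. Importance is low to moderate, since the error is conservative in N and Section 10.2 says that N was set by budget and feasible accrual. The figure should still be corrected and should not be cited as the sensitivity of the planned test.

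**What to change.** Restate Section 10.2 on the randomised N, for example:

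> App opens are logged passively and analysed in all randomised participants. With 500 randomised (250 per arm), SD 45.0 (the core-app value, assumed for both arms), two-sided alpha 0.05 and 80% power, the detectable difference is about 11.3 opens; power for a difference of 13.5 is about 92%. Formal withdrawals or missing covariates may reduce the usable N somewhat. The assumed 70% retention (N = 350) applies to the questionnaire-based endpoints.

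If the sponsor prefers to keep 13.5 at N = 350, label it as a deliberately cautious figure with respect to N only, not the SD.

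The cost is a text change in Section 10.2. Enrolment, data collection and analysis stay as they are.
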